1.0 Objectives

Primary Objective

To evaluate the safety of tagraxofusp in patients with blastic plasmacytoid dendritic cell neoplasm (BPDCN) after autologous (auto) or allogeneic (allo) hematopoietic cell transplantation (HCT).

Secondary Objectives

1. To estimate progression-free survival (PFS) in patients with BPDCN receiving maintenance therapy with tagraxofusp after auto-HCT or allo-HCT.
2. To estimate the overall survival (OS) in patients with BPDCN receiving maintenance therapy with tagraxofusp after auto-HCT or allo-HCT.

2.0 Background and Rationale

BPDCN is a rare hematologic malignancy. The exact incidence is unknown because of changing nomenclature over time and a variety of clinical presentations. Nevertheless, it is estimated that BPDCN accounts for approximately 0.44% of all hematologic malignancies and approximately 0.7% of cutaneous lymphomas as misdiagnosed cases. When coupled with accurately diagnosed cases, the incidence is estimated at about 500 new cases, or more, in the U.S. per year.¹ Males are more commonly affected by BPDCN with a male/female ratio of 3.5/1 and the median age at diagnosis is 66 years.²

Pathogenesis: BPDCN arises from precursors of myeloid origin, the plasmacytoid dendritic cells (pDC; type 2 dendritic cells)³. There is no single genetic abnormality that has been identified as the hallmark of BPDCN, however, a wide array of chromosomal aberrations has been described including a complex karyotype with deletions on chromosomes 5q21 or 5q34 (72%), 12p13 (64%), 13q13-q21 (64%), 6q23-qter (50%), 15q (43%) and 9 (28%) and sporadic genetic alterations affecting RB1, LATS2, CDKN1B, CDKN2A, and TP53 gene.³ In addition, TET24 and FLT3-ITD1 mutations have also been described in the literature.

Clinical presentation: The clinical behavior of BPDCN is usually aggressive. Skin lesions are frequently the initial manifestation of the disease, prompting medical advice⁵, with the face or scalp commonly affected.⁶ Without further therapy, the disease can rapidly progress and result in cytopenias due to bone marrow involvement, lymphadenopathy, and splenomegaly.⁵ Some patients present with disseminated disease at the outset, with multi-organ involvement. In a large analysis of patients with BPDCN with leukemic presentation, 23% did not have any skin lesions.¹ The blasts can be frequently identified in the blood but hyperleukocytosis is not common.⁵ Other reported sites of involvement include central nervous system (CNS), eyes, paranasal cavities, tonsils, lungs, and soft tissues.⁵ The neuromeningeal involvement ranges between 4-9% at diagnosis and 17-33% at relapse.⁵

Immunophenotype: BPDCN tumor cells express CD4 and CD56 (WHO classification, 2017). In addition, the expression of at least one pDC-associated marker, BDCA-2 (blood dendritic cell antigen-2, also termed CD303, CLEC4E), CD123 (also termed interleukin-3 alpha-chain, IL3RA), TCL1 (also termed TCL1A)], or SPIB is needed⁵. Tumor cells lack marker expression for B cells, T cells, myeloid or monocytic cells, and NK cells⁵. CD5, CD7, CD33, and cytoplasmic CD3 may be positive in some cases.⁵

Diagnosis: The diagnosis of BPDCN can be challenging due to lack of specific chromosomal abnormalities. Several immunophenotypic variations have been described⁵. A large series of more than 300 published cases suggested that CD123, CD4, CD56, and TCL1 are the most reliable markers to establish the diagnosis of BPDCN.⁷

Differential diagnosis: BPDCN needs to be differentiated from extranodal (nasal-type) CD56+ NK/T-cell lymphoma (often associated with EBV), cutaneous T-cell lymphoma (usually do not express CD56, CD123, and BDCA2), CD33+AML CD4+/CD56+, undifferentiated AML, AML with myelomonocytic/monocytic differentiation, or ambiguous lineage leukemia (most AML cases are usually positive for MPO and express myeloid antigens such as CD13, CD15, and CD117).⁵

2.1 Treatment of BPDCN

2.1.1 Tagraxofusp

Tagraxofusp (SL-401), a targeted therapy directed to CD123 (the a subunit of the IL3 receptor). Tagraxofusp is comprised of recombinant human interleukin-3 (IL-3) fused to a truncated diphtheria toxin payload. It is composed of IL3 fused via a Met-His linker to the catalytic and translocation domains of a truncated diphtheria toxin (DT).¹⁴⁻¹⁹ The IL3 domain of tagraxofusp binds to its natural receptor, IL3 receptor which is then internalized, leading to translocation of the DT A fragment to the cytosol, followed by ADP ribosylation of elongation factor 2, inactivation of protein synthesis, and cell death.¹⁴ Tagraxofusp inhibits protein synthesis and DT-GMCSF fusion proteins have been shown to active and subsequently kill leukemic cells in the resting G0 phase.²⁰ BPDCN blasts overexpress CD123, and tagraxofusp demonstrated impressive preclinical and, subsequently, clinical results.

Delettre et al. assessed the cytotoxicity of tagraxofusp in BPDCN patient-derived cell lines (CAL-1 and GEN2.2) and primary BPDCN cells isolated directly from patients (n = 12).²¹ Cells were treated for 18 or 48 hours with tagraxofusp single agent and were then compared cells treated with other cytotoxic agents. Cells rerated with tagraxofusp at concentrations substantially lower than peak concentrations achieved in patients, induced a 92% decrease in viability of BPDCN cell lines and 80% in primary BPDCN cells, more effective than most chemotherapeutic agents. Furthermore, NOD-SCID mice were treated with 2Gy radiation followed by injection of GEN 2.2 cells. Mice were then treated with tagraxofusp at clinically relevant doses. The median OS was significantly longer in mice receiving therapy with tagraxofusp vs. untreated controls (53 days vs. 15 days, respectively).

The first clinical experience of tagraxofusp in patients with BPDCN was in a Phase 1/2 study, in which 11 patients with BPDCN received a single course of 12.5 mcg/kg IV over 15 minutes daily for up to 5 doses (Frankel et al).¹⁴ Seven of 9 evaluable first-line or relapsed/refractory BPDCN patients (78%) had major response (5 CR and 2 PR) with a single course of tagraxofusp. The

Reference Location, N	Diagnostic criteria	Treatment	CR rate	Response duration	Proportion bridged to SCT	Survival from diagnosis
		treatment x 2	(37%) 17/41 (41%) ^d			
Poret (2015) France N=86	-	AML-like x 19 ALL-like x 17 CHOP-like x 16 NK/T-like x 16 Other x 12	34/80 (43%)	Median DOR 8-14 months across the different treatments	34/80 (43%)	Median = 8 months
Feuillard (2002) France N=23	CD4+/CD56+	Polychemotherapy	18/23	Median	2/20	Median =
	DC2 cells	py N=2 untreated	(78%)	DOR = 9 months	(10%) adults	12 months
Petrella (2005) France/ Netherlands N=30	CD4+/CD56+ (CD123 PDCs)	Polychemotherapy N=2 untreated	21/28 ^e (78%)	Median DOR = 11 months	-	Median for those treated = 13 months

a = Aggressively treated patients.

b = All treated patients (including palliative cases).

c = After induction therapy.

d = After consolidation therapy.

e = 21/28 patients showed a “good response”. The term “CR” was not used.

2.2.3 Autologous HCT

The data regarding auto-HCT in BPDCN is limited to small case series. There is no consensus on optimal conditioning regimens. In a report, Reimer et al.¹⁶ treated 4 patients with Cyclophosphamide-Total body irradiation (TBI) +/- Etoposide. Three patients died, all from disease relapse. One patient was alive and in CR. In another series of 6 patients by Suzuki et al.¹⁷, median survival was 13.5 months with auto-HCT, however, the conditioning regimen was not specified. In a recent analysis by Kharfan-Dabaja et al.¹⁵, outcomes of 8 patients with BPDCN who underwent auto-HCT were reported. Five of the 8 patients were in CR at the time of auto-HCT. Median age was 67 (45-72) years. One-year PFS and OS were 11%. The median PFS and OS was 12 months for both endpoints.

2.2.4 Allogeneic HCT

The outcomes of BPDCN are more favorable in patients receiving allo-HCT, with long-term remissions more likely in patients who receive SCT in CR.¹⁸ In an Italian study by Pagano et al.,¹

43 patients were retrospectively analyzed. In the 6 patients that received allo-HCT the OS was 22.7 months (range 12-32.9) compared to the non-transplanted patients in whom the OS was 7.1 months (p=0.03). In a registry report from the European Group for Blood and Marrow Transplantation (EBMT), 34 patients with BPDCN who received allo-HCT [myeloablative conditioning (MAC) in 74%; 56% in CR1) had a 3-year cumulative incidence of relapse, disease-free survival (DFS), and OS of 32%, 33%, and 41%, respectively.¹ Three-year non-relapse mortality (NRM) was 30%. Patients who underwent allo-HCT in CR1 trended toward better 3-year DFS (36%) and OS (52%) compared with patients who underwent allo-HCT during more advanced disease (DFS, 26%; OS, 29%). All patients who received reduced intensity conditioning (RIC) experienced early relapse or early death and no patient achieved long-term disease control. In a more recent report, outcomes of 37 patients with BPDCN undergoing allo-HCT at different centers in the US were analyzed.¹ The median age was 50 (range: 14-74) years. One-year and 3-year OS was 68% and 58%, respectively. Three-year OS in patients receiving allo-HCT in CR1 was 74% vs 0% in patients transplanted beyond CR1 (p < 0.0001).

[figure not shown]
In summary, the available data suggest that long-term remission can be expected in approximately 50% of patients undergoing allo-HCT. The outcomes are significantly superior if patients are transplanted in CR1. However, the relapse rate remains a major concern and strategies are needed to minimize this risk.

2.3 Rationale for tagraxofusp use in this study

As evident from the above data, BPDCN is an aggressive disease with limited therapeutic options. Patients undergoing allo-HCT can have long-term remissions, however, despite allo-HCT the relapse rate remains high. BPDCN blasts overexpress CD123 and tagraxofusp, which targets the IL-3 receptor has shown impressive clinical activity with unprecedented response rates. This study intends to assess the safety and clinical activity of tagraxofusp in patients with BPDCN post-HCT, in attempt to reduce the rate of post-HCT relapse and improve OS.

2.3.1 Background drug information (Tagraxofusp)

Tagraxofusp is a 524- amino acid recombinant fusion protein expressed in *Escherichia coli* from a hybrid gene comprised of a DNA sequence of human IL-3 recombinantly fused to a truncated DT payload engineered such that IL-3 replaces the native DT receptor-binding domain. In this way, the IL-3 domain of tagraxofusp directs the cytotoxic truncated DT payload to cells that express CD123. After binding to the CD123, tagraxofusp is internalized by receptor-mediated endocytosis and localized to early endosomes. The translocation domain of DT changes conformation in the acidic environment of the endosome, and the RXRR motif (residues 191-194) located between the catalytic and translocation domains of DT is cleaved by endosomal furin. The translocation domain of DT then inserts into the endosomal membrane. As the TAT-like domain of DT (residues 201-230) interacts with cytosolic heat shock protein 90 (Hsp90) and thioredoxin reductase, the catalytic domain (A fragment) unfolds, is reduced, and translocates to the cytosol. Upon release into the cytosol, the A fragment refolds and catalytically inactivates cellular protein synthesis by adenosine diphosphate (ADP)-ribosylating the diphthamide residue in domain IV of elongation factor 2 (EF-2), leading to apoptosis (Investigator Brochure).

2.3.2 Safety data

The most common individual treatment emergent adverse events (TEAEs) reported to date with tagraxofusp, regardless of dose, were ALT increased (69 patients, 55%) and AST increased (68 patients; 54%); hypoalbuminemia (66 patients; 53%); fatigue (61 patients, 49%); nausea (58 patients; 46%); peripheral edema (55 patients; 44%); pyrexia (54 patients; 43%); thrombocytopenia (44 patients; 35%), and headache and hyperglycemia (each 38 patients; 30%). A summary of the most common (i.e.; incidence ≥10%) TEAEs reported among tagraxofusp -treated patients, regardless of dose, is presented in Table 2. See Version 4.0 of the SL-401 Investigators Brochure for additional safety information.

Table 2. Most Common (≥ 10%) Treatment-Emergent Adverse Events, Overall and by Indication/Study, by MedDRA Preferred Term (Safety Population)

MedDRA Preferred Term	Stemline-Sponsored Study				Total	
	Study 0114 (BPDCN)	Study 0114 (AML)		Study 0314		
		(N=47) n (%)	(N=49) n (%)	(N=14) n (%)		
At least 1 TEAE	47 (100.0)	49 (100.0)	14 (100.0)	15 (100.0)	125 (100.0)	
Alanine aminotransferase increased	30 (63.8)		30 (61.2)	6 (42.9)	3 (20.0)69 (55.2)	
Aspartate aminotransferase increased	28 (59.6)		33 (67.3)	5 (35.7)	2 (13.3)68 (54.4)	
Hypoalbuminemia	26 (55.3)		30 (61.2)	7 (50.0)	3 (20.0)66 (52.8)	
Fatigue	21 (44.7)		27 (55.1)	6 (42.9)	7 (46.7)61 (48.8)	
Nausea	21 (44.7)		26 (53.1)	6 (42.9)	5 (33.3)58 (46.4)	
Oedema peripheral	24 (51.1)		19 (38.8)	3 (21.4)	9 (60.0)55 (44.0)	

		Stemline-Sponsored Study			
	Study 0114 (BPDCN)	Study 0114 (AML)	Study 0214	Study 0314	Total
Pyrexia	21 (44.7)		22 (44.9)	5 (35.7)	6 (40.0)54 (43.2)
Thrombocytopenia	23 (48.9)		11 (22.4)	6 (42.9)	4 (26.7)44 (35.2)
Headache	12 (25.5)		16 (32.7)	4 (28.6)	6 (40.0)38 (30.4)
Hyperglyc1emia	17 (36.2)		17 (34.7)	3 (21.4)	1 (6.7)38 (30.4)
Chills	16 (34.0)		12 (24.5)	5 (35.7)	3 (20.0)36 (28.8)
Dyspnea	6 (12.8)		18 (36.7)	3 (21.4)	9 (60.0)36 (28.8)
Anemia	11 (23.4)		13 (26.5)	3 (21.4)	7 (46.7)34 (27.2)
Hypotension	13 (27.7)		16 (32.7)	2 (14.3)	3 (20.0)34 (27.2)
Decreased appetite	12 (25.5)		15 (30.6)	2 (14.3)	4 (26.7)33 (26.4)
Weight increased	18 (38.3)		11 (22.4)	3 (21.4)	1 (6.7)33 (26.4)
Vomiting	8 (17.0)		14 (28.6)	3 (21.4)	5 (33.3)30 (24.0)
Diarrhea	7 (14.9)		13 (26.5)	3 (21.4)	6 (40.0)29 (23.2)
Dizziness	8 (17.0)		12 (24.5)	3 (21.4)	6 (40.0)29 (23.2)
Back pain	12 (25.5)		10 (20.4)	2 (14.3)	4 (26.7)28 (22.4)
Constipation	11 (23.4)		10 (20.4)	2 (14.3)	4 (26.7)27 (21.6)

		Stemline-Sponsored Study			
	Study 0114 (BPDCN)	Study 0114 (AML)	Study 0214	Study 0314	Total
Capillary leak syndrome	9 (19.1)	10 (20.4)		2 (14.3)	4 (26.7)25 (20.0)
Hypokalemia	10 (21.3)	11 (22.4)		1 (7.1)	3 (20.0)25 (20.0)
Febrile neutropenia	5 (10.6)	17 (34.7)		1 (7.1)	023 (18.4)
Insomnia	7 (14.9)	8 (16.3)		2 (14.3)	6 (40.0)23 (18.4)
Cough	3 (6.4)	13 (26.5)		2 (14.3)	4 (26.7)22 (17.6)
Hypocalcemia	11 (23.4)	8 (16.3)		1 (7.1)	2 (13.3)22 (17.6)
Tachycardia	7 (14.9)	10 (20.4)		2 (14.3)	2 (13.3)21 (16.8)
Pain in extremity	5 (10.6)	8 (16.3)		1 (7.1)	5 (33.3)19 (15.2)
Hyponatremia	9 (19.1)	7 (14.3)		1 (7.1)	1 (6.7)18 (14.4)
Neutropenia	8 (17.0)	7 (14.3)		2 (14.3)	1 (6.7)18 (14.4)
Anxiety	9 (19.1)	4 (8.2)		0	4 (26.7)17 (13.6)

Hypertension	10 (21.3)	5 (10.2)	0	2 (13.3)17 (13.6)
Epistaxis	3 (6.4)	11 (22.4)	1 (7.1)	1 (6.7)16 (12.8)
Blood alkaline phosphatase increased	5 (10.6)	9 (18.4)	1 (7.1)	015 (12.0)
Blood lactate dehydrogenase increased	5 (10.6)	8 (16.3)	2 (14.3)	015 (12.0)
Abdominal pain	4 (8.5)	5 (10.2)	2 (14.3)	3 (20.0)14 (11.2)
Blood creatinine increased	6 (12.8)	6 (12.2)	2 (14.3)	014 (11.2)
Hypoxia	3 (6.4)	6 (12.2)	1 (7.1)	3 (20.0)13 (10.4)
Myalgia	1 (2.1)	8 (16.3)	2 (14.3)	2 (13.3)13 (10.4)

In response to the initial case of Grade 5 CLS, which occurred in a patient with BPDCN treated at the 7 mcg/kg dose level early in the clinical program in Study SL-401-0114, all tagraxofusp protocols were amended to exclude patients with left ventricular ejection fraction (LVEF) below the institutional lower limit of normal, and specify that tagraxofusp infusions should be withheld for patients who have an increase in body weight during the dosing period or other potential early evidence of CLS. After the occurrence of Grade 4 CLS, additional precautions were implemented in all tagraxofusp protocols, including instructions that tagraxofusp dosing cease within a given cycle in the setting of substantial albumin reductions or Grade 3 transaminase elevations. The second Grade 5 case of CLS occurred in a patient with AML treated with tagraxofusp at the 16 mcg/kg dose level, in Study STML-401-0114, a dose level above the MTD determined in that study of 12 m/kg/day.

2.3.3 Carcinogenesis, Mutagenesis, and Impairment of Fertility

At present, reproductive and developmental toxicology studies have not been performed for tagraxofusp; consequently, it is recommended that females of childbearing potential and sexually active males use adequate birth control during study participation and for 2 months after the last dose of tagraxofusp.

3.0 Patient Eligibility

3.1 Inclusion criteria

1. Eligible patients will be aged \geq 18 years. Pediatric patients age 2 years and older will be considered on a case by case basis.
2. Diagnosis of Blastic Plasmacytoid Dendritic Cell Neoplasm (BPDCN) according to WHO classification or confirmed by hematopathology.^{24,25}
3. The patients must be in partial response or better (see Appendix A.).
4. $>$ 30 days post-transplant without active or chronic infections.
5. Karnofsky performance status \geq 60%; Lansky \geq 60 (see Appendices B. and C.).

6. LVEF \geq institutional lower limit of normal by MUGA scan or echocardiogram within 30 days of first protocol treatment.
7. Pulmonary function: DLCO, FEV1, FVC $> 40\%$ of predicted value (corrected for hemoglobin) within 3 months of registration.
8. Adequate organ function:
 - a. Serum creatinine ≤ 1.5 mg/dL (133 mmol/L).
 - b. Serum albumin ≥ 3.2 g/dL (or ≥ 32 g/L) without IV albumin within the previous 72 hours.
 - c. Bilirubin $\leq 1.5 \times$ the upper limit of normal ([ULN] except patients with Gilbert syndrome in whom bilirubin level of $> 1.5 \times$ ULN will be allowed).
 - d. AST and ALT ≤ 2.5 times ULN.
 - e. Hemoglobin ≥ 8 g/dL with or without transfusion in the last 7 days.
 - f. Absolute neutrophil count (ANC) ≥ 1000 without GCSF or GM-CSF in the last 2 weeks prior to screening.
 - g. Platelets $\geq 50,000$ /mL.
9. For allo-HCT, no \geq grade 2 visceral (gut or liver) acute GVHD and no \geq grade 3 or any other acute GVHD (Patients with chronic GVHD will be allowed at the discretion of the investigator).
10. Patient agrees to use acceptable contraceptive methods for the duration of time in the study, and to continue to use acceptable contraceptive methods for 2 months after the last tagraxofusp infusion.
11. Woman of child bearing potential (WOCBP) with a negative serum or urine pregnancy test within 14 days of tagraxofusp treatment.
12. Patient or patient's legal representative, parent(s) or guardian able to sign informed consent.
13. The patient can adhere to the study visit schedule and other protocol requirements, including follow-up for survival assessment.

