4.3 Pre-medication

Approximately 60 minutes prior to receiving tagraxofusp.

- Acetaminophen 650 mg PO
- Diphenhydramine 50 mg IV
- Methylprednisolone 50 mg IV (or equivalent dosage of another corticosteroid)
- Ranitidine 50 mg IV (or equivalent dosage of another H2-histamine antagonist)
- Ondansetron 16 mg IV

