4.5 Route and Administration

Tagraxofusp is administered by IV infusion via syringe pump over 15 minutes. Prior to infusion, venous access should be established and maintained with sterile 0.9% Sodium Chloride Injection, USP. The total infusion time will be controlled using a syringe pump to deliver the entire dose over 15 minutes.

Attach the tagraxofusp syringe containing the patient's dose to one port and the saline flush syringe to the other port of a Smith's Medical Y connector or equivalent. Clamp off the ports until needed. Attach the opposite end of the Y connector to the microbore tubing. Attach an in-line filter to the opposite end of the microbore tubing. Prime the saline port of the Y connector up to the intersection and clamp shut until the saline flush is required. Next, prime the entire administration set up with the diluted tagraxofusp dose so that it is ready to attach inline. When the tagraxofusp syringe is empty, remove it from the pump and place the saline flush syringe in the syringe pump. Open the clamp on the saline flush side of the Y connector and resume infusion via the syringe pump at the pre-specified flow. Note that the flush syringe will not be emptied entirely at the end of the 15-minute infusion, since it is just intended to push remaining tagraxofusp out of the infusion line to complete drug delivery.

The dose of tagraxofusp will be dependent upon the patient's body weight in kg. The dose for subsequent cycles is to be recalculated only if there is a 10% change in body weight from baseline. The aliquot is calculated from the mg/kg dose x patient weight in kg (all patient doses are calculated in mg/kg body weight). Dose changes should only occur once a cycle has been completed. Intra-cycle dose modifications are not permitted.

Inpatient admission for cycle 1 only (day 1 or one day before day 1). After cycle 1, Tagraxofusp can be administered in the inpatient setting or in a suitable outpatient ambulatory care setting that is equipped for intensive monitoring of patients with hematopoietic malignancies undergoing treatment, per the discretion of the investigator and institutional guidelines and capabilities.

Observation post-dosing should continue until it is clear that the patient does not have evidence/symptoms of capillary leak syndrome (e.g., no weight gain, edema, hypotension, or decrease in albumin) or hypersensitivity reaction. Participants will be monitored as described in Section 5.0, Evaluations During Study.

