Supportive care is permitted according to standard institutional/department of MD Anderson Stem Cell Transplantation and Cellular Therapy protocols.

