4.8 Procedures During Dosing Period

Monitor vital signs and check albumin, transaminases, and creatinine prior to preparing each dose of tagraxofusp. During each cycle, testing and procedures that may result in withholding of a scheduled tagraxofusp infusion, largely based on unresolved manifestations of fluid retention and/or other relevant acute toxicities during daily dosing, are described below. Details are presented in Table 3.

Table 3: Recommended Dose Modifications

Parameter	Severity Criteria	Dose Modification
Serum albumin	Serum albumin < 3.5 g/dL or reduced ≥ 0.5 g/dL from value measured prior to initiation of the current cycle	See CLS Management Guidelines (Appendix D.)
Body weight	Body weight increase ≥ 1.5 kg over pretreatment weight on prior treatment day	See CLS Management Guidelines (Appendix D.)
Aspartate aminotransferase (AST) or alanine aminotransferase (ALT)	ALT or AST increase > 5 times the upper limit of normal	Withhold tagraxofusp until transaminase elevations are ≤ 2.5 times the upper limit of normal.
Serum creatinine	Serum creatinine > 1.8 mg/dL (159 micromol/L) or creatinine clearance < 60 mL/minute	Withhold tagraxofusp until serum creatinine resolves to ≤ 1.8 mg/dL (159 micromol/L) or creatinine clearance ≥ 60 mL/minute.
Systolic blood pressure	Systolic blood pressure ≥ 160 mmHg or ≤ 80 mmHg	Withhold tagraxofusp until systolic blood pressure is < 160 mmHg or > 80 mmHg.
Heart rate	Heart rate ≥ 130 bpm or ≤ 40 bpm	Withhold tagraxofusp until heart rate is < 130 bpm or > 40 bpm.
Body temperature	Body temperature $\geq 38^\circ\text{C}$	Withhold tagraxofusp until body temperature is $< 38^\circ\text{C}$.

Parameter	Severity Criteria	Dose Modification
Hypersensitivity reactions	Mild or moderate	Withhold tagraxofusp until resolution of any mild or moderate hypersensitivity reaction. Resume tagraxofusp at the same infusion rate.
	Severe or life-threatening	Discontinue tagraxofusp permanently.

Except in conditions specified above, tagraxofusp may be re-administered subsequently in the same cycle, pending normalization of the abnormalities and pending evidence of stabilization of the underlying clinical conditions resulting in these abnormalities. Postponed doses may be administered within a 10-day period following the initial day of treatment within a cycle.

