4.9 Management of Specific Toxicities Capillary leak syndrome (CLS)

Capillary leak syndrome (CLS) is associated with vascular endothelial injury related to tagraxofusp administration and often occurs 3-8 days after initiation of treatment.

See Appendix D. for management of CLS and associated symptoms (hypoalbuminemia, edema, weight gain and hypotension).

In the setting of delays secondary to findings consistent with CLS (i.e., in the setting of resolved hypotension, tachycardia, increased weight, or albumin reductions of a magnitude lower than those warranting withholding of tagraxofusp for the duration of a given cycle), subsequent tagraxofusp is to be administered on days subsequent to the identification of the abnormality (not the same day), pending determination by the investigator that there is no/minimal evidence of ongoing CLS and pending discussion with the PI.

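### Children from age 2 may be enrolled, but Section 4.3 lists only flat premedication doses with no weight or age rule

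*Combined protocol and SAP*

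**What the plan says.** Section 3.1, item 1 admits adults and then opens the trial to children: "Pediatric patients age 2 years and older will be considered on a case by case basis". Other items are adapted for them: item 5 gives a Lansky score beside the Karnofsky score, and item 12 lets a parent or guardian sign consent.

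Section 4.3 lists what is given about an hour before tagraxofusp. The entries are fixed amounts, such as "Acetaminophen 650 mg PO" and "Ondansetron 16 mg IV". Diphenhydramine, methylprednisolone and ranitidine are each listed at 50 mg. The only flexibility is in entries such as "Methylprednisolone 50 mg IV (or equivalent dosage of another corticosteroid", which allows a change of drug within the class. Ranitidine has the same allowance for another H2 antagonist.

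Tagraxofusp is scaled to body size. Section 4.4 gives 9 or 12 mcg/kg, and Section 4.5 says that "all patient doses are calculated in mg/kg body weight". Section 4.5 also has a general clause: "Supportive care is permitted according to standard institutional/department of MD Anderson Stem Cell Transplantation and Cellular Therapy protocols".

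On a side point, one row of Table 3 (Section 4.8) uses a fixed weight gain as a prompt for capillary leak syndrome (CLS): "Body weight increase ≥ 1.5 kg over pretreatment weight on prior treatment day". That row sends the reader to Appendix D.

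**The concern.** Eligibility was adapted for children, and the study drug adjusts to body size by itself. The premedication list does neither. Staff who follow Section 4.3 exactly would give a child of 20 kg the same five amounts as an adult, on each dosing day. At stake is the safety of any child enrolled, not the design or its estimates.

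**Working it through.** There is no figure in the plan to reproduce. The check compares sections and then divides each fixed dose by body weight.

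**Inputs from the protocol.** Fixed doses (Section 4.3): acetaminophen 650 mg; three drugs at 50 mg each; ondansetron 16 mg. Tagraxofusp 12 mcg/kg from patient 4 onward (Section 4.4). Dosing on Days 1-3 in Cycles 1-4 and on Days 1-2 afterward (Section 4.4), with up to 24 cycles for patients in CR or CRc before any extension (Section 4.2).

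**Inputs assumed.** The documents give no body weights. I use 70 kg for an adult, with a range of 60 to 90 kg, and 50, 30 and 20 kg for younger patients.

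**Step 1: dose per kg = fixed dose / weight.**

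| Weight | Acetaminophen | Each 50 mg drug | Ondansetron |
|---|---|---|---|
| 70 kg | 650/70 = 9.3 mg/kg | 50/70 = 0.71 mg/kg | 16/70 = 0.23 mg/kg |
| 50 kg | 650/50 = 13.0 | 50/50 = 1.0 | 16/50 = 0.32 |
| 30 kg | 650/30 = 21.7 | 50/30 = 1.7 | 16/30 = 0.53 |
| 20 kg | 650/20 = 32.5 | 50/20 = 2.5 | 16/20 = 0.80 |

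**Step 2: multiple of the adult per-kg dose = adult weight / patient weight.** This is the same for all five drugs.

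- 30 kg: 70/30 = 2.3 (60/30 = 2.0 to 90/30 = 3.0).
- 20 kg: 70/20 = 3.5 (60/20 = 3.0 to 90/20 = 4.5).
- 50 kg: 70/50 = 1.4 (60/50 = 1.2 to 90/50 = 1.8). A 50 kg adult has this same multiple, so it says nothing specific to children.

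**Step 3: contrast with the study drug.** At 12 mcg/kg the daily tagraxofusp dose is 12 × 70 = 840 mcg at 70 kg and 12 × 20 = 240 mcg at 20 kg. The study drug falls with weight and the premedication does not.

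**Step 4: how often it recurs.** Planned dosing days are 4 × 3 = 12 in Cycles 1-4 and 12 + 20 × 2 = 52 over 24 cycles.

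**Step 5: search for a rule elsewhere.** The supportive-care clause in Section 4.5 gives no pediatric dose and does not amend Section 4.3. The concomitant-medication text in Section 6.0 gives none either; it says only that such drugs are standard of care and that no data on them are captured. The appendices were not supplied. The protocol cites them for response criteria, performance scales, CLS management and the letter to the local physician, and Section 4.3 refers to none of them.

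**Side point: the Table 3 weight row.** A gain of 1.5 kg is 1.5/70 = 2.1% of body weight at 70 kg, 1.5/30 = 5.0% at 30 kg and 1.5/20 = 7.5% at 20 kg. A fixed gain is therefore a less sensitive prompt in a small child.

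**The case against.** The strongest reply is that no one would give these doses to a small child. Each child is considered individually, Cycle 1 is given in hospital, and the institution's own supportive-care protocols apply. Item 7 of Section 3.1 also requires DLCO, FEV1 and FVC with no pediatric exemption, which makes very young patients less likely. Where the transplant series in Section 2.2 state an age range, the youngest patients were 14 (37 allogeneic transplants) and 45 (8 autologous transplants). All of this stands, and it keeps the reach small. It does not supply a rule. Case-by-case review decides entry, not dose, and the protocol itself names age 2 as the floor.

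A second reply is that the Section 4.5 sentence on mg/kg dosing covers every drug. In context it explains how the tagraxofusp aliquot is calculated, so it does not reach Section 4.3.

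A third reply is that a per-kg multiple does not measure harm. That is correct. The documents contain no pediatric dose limit and the weights are assumed. A reader might infer from the multiples that the plan prescribes a toxic dose. The documents do not support that; they support only that the stated rule does not scale.

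A reader might also infer from the Table 3 row that CLS would be missed in children. That goes too far. The row leads to Appendix D, which may already adapt management for children. Section 4.9 refers to the same appendix "for management of CLS and associated symptoms (hypoalbuminemia, edema, weight gain and hypotension", with no kilogram threshold. The albumin trigger does not depend on size, and Section 4.5 continues observation after dosing until there is no sign of CLS.

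**Conclusion.** The gap is real and minor. Section 4.3 states a complete dosing rule that, applied exactly to a patient whom Section 3.1 allows in, gives a small child about 2.3 times (30 kg) to 3.5 times (20 kg) the per-kg premedication of a 70 kg adult. These figures rest on assumed weights and on staff following the text without adjustment. Any children enrolled are likely to be few.

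A reader might infer that the primary endpoint or the toxicity rule is compromised. Neither is: the sample size of 20, the stopping boundaries and the confidence intervals do not depend on premedication doses. Nor does the point call for a minimum body weight. No such cut-off has a source in the documents, and one set by weight alone would also catch light adults. This is a cheap improvement to patient safety in a rare subgroup.

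**What to change.** Add one sentence to Section 4.3: *For patients under 18 years, give each premedication by weight per institutional pediatric dosing, not exceeding the dose listed above.* Because the rule is tied to age, adult dosing is unchanged and no one is excluded. The cost is one sentence.

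Optional, for patients under 18 only and subject to what Appendix D already says: change the Table 3 weight row to *1.5 kg or an investigator-set percent of body weight, whichever is smaller*. The percent should be chosen on clinical grounds, not scaled from an adult. The downside is a few more held doses in a child. Section 4.9 rules out same-day dosing after a CLS-related delay, and a dose never given counts against the primary endpoint of 75% of planned doses (one patient is 1/20 = 5 percentage points). Section 4.8 softens this by allowing postponed doses within 10 days of the first treatment day of the cycle.
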